8.Experimental design: : A two-arm parallel trial design was carried out.The participants who underwent PCNL with one-handed lithotripsy were selected as the experimental group, and the participants who underwent traditional PCNL were selected as the control group.Prospective exploration studies were conducted on a 1:1 basis.

9.Site: This was a single-center study conducted at the First Affiliated Hospital of the University of South China

10.. Inclusion and exclusion criteria:1.Participants who met the the applications of PCNL surgery in the 2019 Chinese Guidelines for the Diagnosis and Treatment of Urological Diseases; 2. Participants who agree to undergo PCNL with one-handed lithotripsy.Exclusion Criteria: 1).Obvious surgical contraindications, such as severe heart and lung insufficiency, abnormal coagulatory function.2) If the following variations occurred during the operation: a finding that pyonephrosis demanded the treatment of nephrostomy,channel bleeding that was required to maintain a nephrostomy tube,or incomplete postoperative clinical data will be recorded by the study recruitment flow chart, but not included in the final data analysis

11.Intervention measures:

a. According to the randomization, the same associate chief urologist performed PCNL with one-handed lithotripsy or traditional PCNL;

b.During the perioperative period, participants were given comprehensive blood biochemical examination and imaging evaluation, and antibiotics (second-generation cephalosporins or penicillins) were prophylactic.Participants with hypertension, diabetes and other comorbidities were given relevant drugs to control the tolerable level of surgery.

c. Implementation process of PCNL with one-handed lithotripsy:

a).After general anesthesia, the patient was placed in lithotomy position, routinely

[figure not shown]

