disinfected and covered with towels. Transurethral cystoscopy/ureteroscopy was performed to observe the ureteral opening on the affected side, and the ureteral catheter was retrograde inserted at a depth of 15 to 25cm. Exit the ureteroscope and fix the ureteral catheter on the urinary catheter. Then, the patient was moved to prone position, disinfected again and covered with towel, suffer renal biopsy under ultrasound guided look straight into the target under the calyces, syringe after water injection and suction is smooth, the guide wire guided by micro fascia dilator (Fr16 or Fr18) continuous build percutaneous renal channel expansion. Holmium laser was used for lithotripsy

b). According to different lithotripsy methods, the operation was randomly divided into group 1 (one-handed lithotripsy group): using one hand to control the nephroscope and laser fiber at the same time, the other hand to adjust the depth and angle of the sheath at same time. Group 2 (traditional lithotripsy group) : lithotripsy was carried out by holding the nephroscope with one hand and controlling the laser fiber with the other one. It was often necessary to stop the lithotripsy to adjust the depth and angle of the sheath.

c). After the broken stones were removed, the ureteropelvic opening was located, the guide wire was placed anteriorly, and the ureteral stent was placed under the guidance of the guide wire. After no residual calculi were detected under the nephroscope, the endoscope was removed and the nephrostomy tube was indwelled and fixed. The incision skin is then sutured.

12. Outcome measures : The primary clinical end point are operative time 、 stone clearance rate 、 number of tracts 、 rate of second operation 、 rate of auxiliary procedure 、 intraoperative renal pelvis mucosal injury rate 、 the incidence of postoperative complications (including postoperative fever, bleeding, pain, and changes in renal function; Ureterostone street was formed after operation. Air-fluid chest after operation) ; The secondary clinical end points were operation time, hospital stay, hospital cost.

13. Recruitment flow chart:

14. Sample size: Combined with the number of outpatient calculi patients and the number of PCNL surgeries in our department of Urology each year, we planned to initially include 100 patients with renal and/or upper ureteral calculi who underwent traditional PCNL surgery in our hospital from November 2022 to November 2023, and randomly assigned at 1:1.

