15. Participants: Patients with upper urinary stones attending the Urology Clinic of the First Affiliated Hospital of the University of South China were recruited

16. Allocation sequence generation, allocation hiding, implementation methods: Using the coin toss method, patients with the flip side of the coin were divided into PCNL surgery group using one-handed lithotripsy technique (group 1), and patients with the reverse side of the coin were assigned to the traditional PCNL procedure group (group 2). This process takes place in the operating room

17. Blinding: : In a single-blind approach, patients are told to participate in a clinical trial but are not informed about the specific intervention, while the person administering the intervention is clearly informed.

18. Data collection: The measured data of all the required: : 1. The demographic data, stone characteristics and preoperative baseline data, including the proportion of gender, age, body mass index (BMI) and basic diseases distribution, location, stones, stone maximum cross-sectional area, the longest diameter antler shape proportion and

pelvic effusion width, partial side and puncture operation, etc.2.Data of the main end points included:operative time、 stone clearance rate、 number of tracts、 rate of second operation、 rate of auxiliary procedure、 intraoperative renal pelvis mucosal injury rate、 the incidence of postoperative complications (including postoperative fever, bleeding, pain, and changes in renal function; Ureterostone street was formed after operation. Air-fluid chest after operation) ; Secondary end points included:postoperative renal function changes, operative blood loss, postoperative bleeding rate, postoperative patient pain score, postoperative inflammation changes。

19. Statistical analysis plan: SPSS26.0 statistical software was used for analysis.

Measurement data were expressed as mean \pm standard deviation ($X \pm S$) and t-test was used. Enumeration data were expressed as frequency and percentage by X^2 or Fisher exact test. Rank sum test was used for rank data. $P < 0.05$ was considered statistically significant.

20.Ethical approval: This trial was a human life science and medical study and was approved by the Medical Ethics Committee of the First Affiliated Hospital of the University of South China. (No: 2022111120001)

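### Renal function and inflammation are worded as changes, but the only test given for continuous data is an unadjusted t-test; adjusting the postoperative value for its baseline would be more precise at almost no cost

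*Protocol*

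**What the plan says.** Section 18 of the protocol (data collection) names as secondary end points "postoperative renal function changes, operative blood loss, postoperative bleeding rate, postoperative patient pain score, postoperative inflammation changes". Two of these, renal function and inflammation, are worded as changes. No marker, time point, scale or formula is given for either.

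Section 19 (statistical analysis plan) assigns tests by type of data and not by end point. For continuous data it says "Measurement data were expressed as mean" with standard deviation, "and t-test was used". For categorical data, "Enumeration data were expressed as frequency and percentage" and compared by chi-square or Fisher's exact test. For ordinal data, "Rank sum test was used for rank data". No adjustment for a baseline value appears anywhere.

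Renal function also has a second role. Sections 12 and 18 both place it in a primary end point, "the incidence of postoperative complications (including postoperative fever, bleeding, pain, and changes in renal function". Section 12 gives a different secondary list: "The secondary clinical end points were operation time, hospital stay, hospital cost".

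On preoperative values, Section 11b says that in the perioperative period "participants were given comprehensive blood biochemical examination and imaging evaluation". The baseline list in Section 18 does not name renal function or an inflammation marker, although it is open-ended.

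**The concern.** An end point worded as a change, combined with a t-test for all continuous data, points to a comparison of post-minus-pre differences between arms. That construction subtracts each patient's preoperative value with a fixed weight of 1, however weakly it predicts the postoperative value. When the correlation is weak, the subtraction adds noise. If the t-test is instead applied to the postoperative value alone, the weight is 0 and any predictive information in the baseline is discarded. ANCOVA estimates the weight from the data.

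What is at stake is precision. The planned 100 patients were set from clinic and surgical volume (Section 14), with no effect size, SD or power stated, so nothing in the plan shows that there is precision to spare.

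**Working it through.** **Inputs.** From the protocol: 100 patients planned, 1:1 (Section 14), allocated by coin toss (Section 16); t-test for continuous data and significance at 0.05 (Section 19), taken as two-sided. Not in the protocol, hence assumed and varied: the correlation r between the pre- and postoperative values, and their SDs s0 and s1. There is no power calculation in the plan to reproduce.

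**Formulas.** Per unit of (1/n1 + 1/n2), the large-sample variance of the between-arm difference is:

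- t-test on the change: s0² + s1² − 2·r·s0·s1
- t-test on the postoperative value: s1²
- ANCOVA: s1²·(1 − r²)

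The change score exceeds ANCOVA by (s0 − r·s1)², which is never negative. The ratio of ANCOVA to the t-test on the postoperative value is 1 − r², which is never above 1.

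**Equal SDs, against the change score.** The ratio is (1 − r²)/(2(1 − r)) = (1 + r)/2.

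| r | ANCOVA / change | Patients the change score needs to match ANCOVA with 100 |
|---|---|---|
| 0.2 | 0.60 | 100/0.60 ≈ 167 |
| 0.5 | 0.75 | 100/0.75 ≈ 133 |
| 0.8 | 0.90 | 100/0.90 ≈ 111 |

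In terms of power, for a true difference of 0.5 postoperative SD with 50 per arm, change score against ANCOVA: 56% and 75% at r = 0.3; 71% and 82% at r = 0.5; 90% and 94% at r = 0.7.

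**Larger postoperative spread, against the change score** (s1 set to 1).

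- s0/s1 = 0.5, r = 0.2: change 0.25 + 1 − 0.20 = 1.05; ANCOVA 1 − 0.04 = 0.96; ratio 0.91 (about 109 patients in place of 100).
- s0/s1 = 0.3, r = 0.2: change 0.09 + 1 − 0.12 = 0.97; ANCOVA 0.96; ratio 0.99 (about 101 patients).

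The change score is noisier than ignoring the baseline altogether when r < s0/(2·s1). That threshold is 0.5 with equal SDs but 0.15 at s0/s1 = 0.3.

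**Against the postoperative value alone.** 1 − r² = 0.96, 0.75 and 0.36 at r = 0.2, 0.5 and 0.8, whatever the SD ratio. The two comparisons complement each other: a low r with similar SDs penalises the change score, and a high r penalises the postoperative value.

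**Finite-sample cost.** Estimating the slope multiplies the ANCOVA variance by about 1 + 1/(N − 4), which at N = 100 is 1 + 1/96 = 1.010. This shows as a net loss only where the large-sample ratio is close to 1. One example is a true slope of 1 (s0/s1 = r = 0.5): the large-sample ratio is 0.75/0.75 = 1.00, and a simulation with coin-toss allocation and N = 100 (20,000 runs) gave 1.011. With equal SDs and r = 0.5, the same simulation gave 0.751 against the formula's 0.75.

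**The case against.** The strongest objection is that the protocol nowhere states the analysis being criticised. Section 18 is a data-collection list, and Section 19 names tests by data type. A reader might infer that the stated analysis is a t-test on post-minus-pre differences. That is the natural reading, but it remains an inference: a t-test on the postoperative value, a paired test within arms, or an incidence comparison would also fit the words, and renal function is explicitly counted within complication incidence. This stands, and the point is worded accordingly. It does not remove the point, because ANCOVA is in large samples at least as precise as either between-arm t-test, and a paired test within arms would not compare the arms at all. The incidence reading is weaker for these entries: Section 18 lists renal function changes separately from the complication incidence, and inflammation is not in the complication list.

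Second, a reader might infer that baseline adjustment is always at least as precise. That is a large-sample result; at N = 100 adjustment can lose about 1%.

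Third, the largest gains need equal SDs. If acute inflammation markers spread out after surgery, the gain over the change score can be close to nothing. This also stands; the range is shown above.

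Fourth, a reader might infer bias from chance baseline differences between arms. Under random allocation neither t-test is biased on that account, and chance imbalance is part of the variance already counted, not a second harm.

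Finally, covariate adjustment is often left to a separate SAP, and one may exist. But this protocol fixes a test for continuous data in a section of its own, so the comment is on stated text and not on silence.

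**Conclusion.** The point holds as a matter of efficiency. For renal function and inflammation analysed as continuous measures, the unadjusted t-test in Section 19 is, in large samples, no more precise than ANCOVA on the same marker's baseline, whichever of the two outcomes it is applied to. Against the change score, the variance ratio runs from 0.60 to 0.90 for r from 0.2 to 0.8 with equal SDs, and rises to 0.91 or 0.99 at r = 0.2 when the preoperative SD is 0.5 or 0.3 of the postoperative one. Against the postoperative value alone it is 1 − r². The most that adjustment can cost at N = 100 is about 1% in variance.

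All values of r and of the SDs are assumptions, so the actual gain in this trial is unknown. The matter touches end points that are secondary in Section 18, and the unadjusted comparison remains valid under randomisation. It is a worthwhile improvement, not the repair of a biased or invalid analysis.

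**What to change.** Add one sentence to Section 19: where renal function and inflammation are analysed as continuous measures, the postoperative value is compared between arms by ANCOVA with the same marker's preoperative value as covariate, on the log scale for skewed markers, and the adjusted difference is reported with its 95% CI. Keep the incidence of renal function change as a complication under chi-square or Fisher's exact test.

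For the sentence to be usable, Section 18 should name the markers and the pre- and postoperative time points, and the secondary lists in Sections 12 and 18 should be reconciled, including the double role of renal function.

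The cost is small. Any change already requires a preoperative value, perioperative blood biochemistry is planned (the markers and their timing need confirming), and SPSS, the software named in Section 19, fits the model. No extra patients are needed.

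### Section 19 fixes an unadjusted t-test for operative time although stone burden is measured at baseline: valid, but it gives up precision if stone burden predicts operative time

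*Protocol*

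**What the plan says.** Section 19 of the protocol, headed as the statistical analysis plan, matches tests to data types. Measurement data are summarised by mean and standard deviation, "and t-test was used. Enumeration data were expressed as frequency and percentage by X^2 or Fisher exact test". It names no covariate, stratum or regression model.

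Operative time is measurement data, and Section 12 puts it first among the primary items: "The primary clinical end point are operative time", followed by six others.

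Section 18 lists what is recorded before surgery: "The demographic data, stone characteristics and preoperative baseline data, including the proportion of gender", and later in the same list "stone maximum cross-sectional area, the longest diameter antler shape proportion". That phrase is garbled; antler shape is read here as staghorn shape.

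Section 16 allocates by coin toss and states no stratification: "Using the coin toss method, patients with the flip side of the coin were divided into PCNL surgery group".

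Section 14 sets the size from caseload: "we planned to initially include 100 patients with renal and/or upper ureteral calculi". Section 10 adds that patients with certain intraoperative findings or incomplete data are recorded "but not included in the final data analysis".

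**The concern.** Stone burden is measured before surgery, yet neither the design nor the analysis uses it. If it predicts operative time, the t-test leaves that variation in the error term, and the confidence interval is wider than the collected data allow.

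Such a relation is plausible from the protocol itself. Section 6 covers staghorn, complex and large stones, and Section 11 has the operation end only when no residual stone is seen. One urologist performs both techniques, so differences between surgeons do not contribute to the variation. The strength of the relation is not documented.

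A second consequence concerns chance imbalance. Unstratified coin tossing can leave the arms with different stone burdens, and the plan has no pre-specified way to account for this. An adjusted analysis could still be run later, but covariates chosen after an imbalance has been seen are open to the charge of selection. With about 100 patients, fewer after the Section 10 exclusions, precision that costs no patients is worth having.

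The point concerns operative time only, not the rate endpoints.

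**Working it through.** **Nothing to reproduce.** The protocol states no power, effect size, SD or correlation; 100 is a caseload figure.

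**Inputs from the protocol.** 100 patients at 1:1, so 50 per arm (Section 14); significance at P < 0.05 (Section 19), taken as two-sided.

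**Assumptions.**
- Operative time is in SD units.
- The true effect is d = 0.566 SD (0.5659 unrounded), chosen because it gives 80.0% unadjusted power at 50 per arm.
- R is the multiple correlation of stone area and staghorn shape with operative time within arm, from 0 to 0.6.
- 50 per arm is the upper bound, because Section 10 removes patients. 45 per arm is used as an illustration of what might remain.

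**Unadjusted t-test, 50 per arm.** Degrees of freedom 98; SE = √(2/50) = 0.200; 95% CI half-width = 1.9845 × 0.200 = 0.397. Noncentrality = 0.5659/0.200 = 2.829, and the noncentral t gives power 80.0%.

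**Adjusted model, two covariates.** Degrees of freedom 96. The variance is multiplied by (1 − R²)(1 + 2/95), where 1 + 2/95 is the expected cost of estimating two covariates. So SE = 0.200 × √[(1 − R²)(1 + 2/95)], and the equivalent unadjusted trial size is 100/[(1 − R²)(1 + 2/95)].

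Example, R = 0.5: 0.75 × 1.02105 = 0.7658; SE = 0.200 × 0.8751 = 0.1750; half-width = 1.985 × 0.1750 = 0.347; noncentrality = 0.5659/0.1750 = 3.233; power 89.3%; equivalent size = 100/0.7658 = 130.6.

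| R | Power, 50 per arm | CI half-width (SD) | Equivalent unadjusted N | Power, 45 per arm |
|---|---|---|---|---|
| Unadjusted | 80.0% | 0.397 | 100 | 75.6% |
| 0 | 79.2% | 0.401 | 98 | 74.6% |
| 0.1 | 79.6% | 0.399 | 99 | 75.1% |
| 0.2 | 80.8% | 0.393 | 102 | 76.3% |
| 0.3 | 82.8% | 0.383 | 108 | 78.5% |
| 0.5 | 89.3% | 0.347 | 131 | 85.8% |
| 0.6 | 93.4% | 0.321 | 153 | 90.6% |

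The 45-per-arm column uses the same effect, 86 degrees of freedom and the factor 1 + 2/85. Adjusted power equals unadjusted power at R = 0.145 with 50 per arm and at R = 0.153 with 45.

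**Simulation check.** With coin-toss arms, 100 patients and 12,000 runs per value, adjusted power was 79.2, 80.6, 82.3, 89.1 and 93.3% at R = 0, 0.2, 0.3, 0.5 and 0.6; unadjusted power was 79.6 to 80.1%. In a separate simulation of 20,000 trials per setting, the type I error of the t-test was 0.048 to 0.051 for R² from 0 to 0.5.

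**Chance imbalance.** Take one stone-burden score with correlation ρ with operative time (a different quantity from R). Let Z be the standardised arm difference in the score. Its standard error is 0.2 SD, so |Z| ≥ 1 means that the arms differ by at least 0.2 SD, which happens in 31.7% of trials. The unadjusted false-positive rate is P(|ρZ + √(1 − ρ²)·E| > 1.96), with E an independent standard normal, conditional on Z:

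| ρ | Arms differ by ≥ 0.2 SD (32% of trials) | Otherwise (68%) |
|---|---|---|
| 0.3 | 6.6% | 4.3% |
| 0.5 | 9.2% | 3.1% |
| 0.6 | 10.8% | 2.3% |

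The weighted total is 5.0% in every row; for ρ = 0.5, 0.317 × 0.0917 + 0.683 × 0.0306 = 0.050.

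**The case against.** The strongest reply is that this is not an error. A t-test on two randomised means is valid, and Section 19 does not forbid an adjusted analysis. The benefit depends on a correlation that the protocol does not give: below R of about 0.145 adjustment loses a little power, at 0.2 it gains only 0.8 points, and the attractive gains need R of 0.5 or more. The conditional false-positive rates average back to 5.0% and depend on the same unknown and on a chosen 0.2 SD cut-off.

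All of that is true, and it limits the point to one of efficiency. It does not remove it. Section 19 states the test, so this is a choice made and not a detail left open, and the trade is lopsided: at most about 1 power point lost against about 9 gained at R = 0.5.

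Three further reservations stand:
- The t-test's validity presumes intact randomisation. Exclusions after allocation under Section 10 may depend on technique, and covariate adjustment does not in general repair that.
- Section 12 also lists operation time as secondary. That needs settling separately.
- Staghorn shape is an inference from garbled text and may overlap with stone area, so the second covariate may add little.

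**Conclusion.** The point holds as a loss of precision, not as a bias or an inflated overall error rate. Under the stated assumptions, the 95% CI half-width at 50 per arm changes from 0.397 SD to between 0.401 SD (R = 0) and 0.321 SD (R = 0.6), and power moves from 80.0% to between 79.2% and 93.4%. Whether the gain is trivial or worth some 30 to 50 patients depends on how strongly stone burden predicts operative time, which the protocol does not say. Confidence in the size is therefore moderate. The change should be made, because the possible gain clearly exceeds the worst-case loss.

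**What to change.** In Section 19, make the main analysis of operative time a pre-specified linear model with treatment, stone maximum cross-sectional area and staghorn yes/no.

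- Fix the outcome scale and the form of the area term in advance, not from the trial data. Untransformed operative time keeps the same mean difference as the t-test.
- Use one size measure, and name area or longest diameter before the data are seen.
- State the staghorn definition clearly in Section 18.
- Report the adjusted difference with its 95% CI, and keep the t-test as a sensitivity analysis.
- Leave chi-square or Fisher tests for the rate endpoints.

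Cost: two sentences in Section 19 and a clarified definition in Section 18, with no extra patients, visits or measurements; SPSS 26.0 fits the model. Statistical downside: two degrees of freedom, and 0.8 power points at 50 per arm or 1.0 at 45 if stone burden does not predict operative time.
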